3 QUESTIONS ABOUT BELIEFS AND ATTITUDES

Please answer the following questions about your personal opinions in the context of blood culture sampling for acute adult medical patients with suspected severe infection. There are no right or wrong answers and we are simply interested in your personal attitudes. Please rate your agreement with the questions using the following rating scale:

- 1 = Strongly disagree
- 2 = Disagree
- 3 = Somewhat disagree
- 4 = Neither agree or disagree
- 5 = Somewhat agree
- 6 = Agree
- 7 = Strongly agree

[Questions 3.1-3.20 will be presented in fully randomised order to each participant. Questions for reverse-coding are italicised.]

Attitudes pertaining to the general importance of blood culture sampling

- 3.1 In my role, blood culture sampling benefits patients with suspected severe infections.
- 3.2 Obtaining blood culture samples is a valuable activity that influences treatment choices in patients with suspected severe infection.
- 3.3 The difficulties of obtaining meaningful blood culture samples outweigh the benefits.
- 3.4 I sometimes feel that obtaining blood culture samples is not worthwhile.
- 3.5 Compared to other clinical tasks, I find the activities involved in obtaining blood culture samples to be unpleasant.

Perceptions of subjective norms

- 3.6 Colleagues I respect make time to request or collect blood cultures.
- 3.7 Obtaining blood cultures for every patient with suspected severe infection is part of our normal working culture within my unit of work.
- 3.8 Colleagues I respect value timely blood culture sampling in patients with suspected severe infection.
- 3.9 I feel under pressure from colleagues to prioritise other activities over obtaining blood culture samples for patients with suspected severe infection.

3.10 Where I work, blood culture sampling is not considered valuable for patients with suspected severe infections.

Perceived behavioural control (self-efficacy)

- 3.11 In my experience, there are many practical difficulties in obtaining timely blood culture samples.
- 3.12 I do not feel confident requesting or collecting blood cultures or using blood culture results.
- 3.13 Blood culture sampling is a routine procedure of little technical difficulty.
- 3.14 I often struggle to obtain blood culture samples from patients.
- 3.15 I have not received adequate training or guidance for activities related to blood culture sampling.

Perceived behavioural control (controllability)

- 3.16 Whether or not blood culture samples are obtained is out of my personal control.
- 3.17 There are a lot of factors outside of my control that influence whether or not blood culture samples are obtained.
- *3.18* It is up to me whether blood culture samples are taken from patients with suspected severe infection.
- 3.19 Whether blood cultures are used to inform the treatment of patients with suspected severe infection is beyond my control.
- 3.20 I feel like my personal choices and behaviours matter for the overall success of blood culture sampling for severe infection management.

4 QUESTIONS ABOUT FACTORS THAT AFFECT BLOOD CULTURE SAMPLING

Below is a list of factors that have been suggested as barriers to blood culture sampling for adult patients with suspected severe infection. Please rate to what extent you agree that these factors influence current blood culture sampling practices in acute hospital care in England. There is also an option to include additional factors that you have identified based on your professional experience. Please add as many factors as you consider relevant.

- 1 = Strongly disagree [that this factor influences blood culture sampling]
- 2 = Disagree [that this factor influences blood culture sampling]
- 3 = Somewhat disagree [that this factor influences blood culture sampling]
- 4 = Neither agree or disagree [that this factor influences blood culture sampling]
- 5 = Somewhat agree [that this factor influences blood culture sampling]
- 6 = Agree [that this factor influences blood culture sampling]
- 7 = Strongly agree [that this factor influences blood culture sampling]

[The list of factors will be presented in randomised order to each participant.]

Barriers to requesting blood culture samples

- 4.1 Staff forget to request blood culture samples.
- 4.2 The request to collect a blood culture sample is not always communicated to staff who need to take the sample.

Barriers to collecting blood culture samples

- 4.3 Staff forget to take blood culture samples that have been requested.
- 4.4 Staff find it unpleasant to take blood culture samples.
- 4.5 It is technically difficult to obtain blood culture samples (e.g., due to difficulties with canulation).
- 4.6 Staff are insufficiently skilled or experienced in taking blood culture samples.

4.7 Blood culture kits (bottles, needles, syringes) are not easily available.

Barriers to packaging, storing and transporting samples

- 4.8 There is insufficient knowledge about storage requirements for blood culture samples.
- 4.9 There is insufficient knowledge about the prevention of contamination throughout all stages of blood culture sampling.
- 4.10 Blood samples get delayed during transfer to the laboratories.
- 4.11 Blood samples get lost during transfer to the laboratories.
- 4.12 The location of the nearest microbiology laboratory is inconvenient (e.g., too far away).

Barriers to laboratory testing of blood culture samples

- 4.13 There are concerns about the financial costs of doing too many laboratory tests.
- 4.14 There are concerns about the quality and reliability of laboratory tests.
- 4.15 There is limited laboratory capacity (e.g., due to limited staff, facilities and consumables).

Barriers to using blood culture results

- 4.16 Staff think blood cultures are not useful, because results take too long to come back.
- 4.17 There is a lack of *immediate* clinical value of taking blood culture samples.
- 4.18 Staff think that blood culture results make little difference to patient treatment.

Barriers concerning general attitudes, knowledge and individual staff priorities

- 4.19 Staff members feel too busy to engage in blood culture sampling.
- 4.20 Obtaining blood culture samples is seen as less of a priority than other clinical activities.
- 4.21 There is a perceived lack of evidence that blood culture sampling improves patient care.
- 4.22 Staff do not know enough about how blood cultures affect antibiotic prescribing.
- 4.23 Not enough staff know about national or hospital guidelines around blood culture sampling.
- 4.24 National and hospital blood culture collection guidance is difficult or impractical to follow.
- 4.25 Clinical colleagues don't value blood culture sampling.
- 4.26 Senior colleagues or managers don't value blood culture sampling.

Barriers pertaining to team management and communication

- 4.27 There is a lack of clarity about roles and responsibilities (e.g., it is unclear who is responsible for taking blood culture samples).
- 4.28 The person requesting the blood culture samples is not the one who will receive the results.
- 4.29 The person requesting blood culture samples doesn't find out how these blood culture results inform care later on.

Other barriers

4.30 Other, please specify:	
5 OPEN-ENDED QUESTIONS	

5.1 In your opinion, what actions or interventions might be useful to improve blood culture sampling practice to inform the treatment of patients with acute infection?

5.2 Many thanks for sharing your opinions about blood culture sampling with us. Are there any other thoughts, opinions or suggestions you would like to share about blood culture sampling for patients with suspected severe infection?

APPENDIX 2 - Analysis plan

1) Have any data been collected for this study already?

No, no data have been collected for this study yet.

2) What's the main question being asked or hypothesis being tested in this study?

Q1. Does our newly developed attitude questionnaire capture key components of the Theory of Planned Behaviour within the context of blood culture sampling?

Q2. What are NHS healthcare professionals' attitudes towards blood culture sampling for adult patients with suspected severe infection? Do these attitudes differ by professional role and clinical setting?

Q3. What are predictors of self-reported engagement in clinical activities that form part of the blood culture pathway?

Q3. What are perceived barriers to healthcare staff engaging in clinical activities related to blood culture sampling for managing suspected severe infection? Do these perceived barriers differ by professional role or clinical setting?

H1. Healthcare staff's attitudes around blood culture sampling will map on to a four-factor structure proposed by the Theory of Planned Behaviour: (1) perceived importance, (2) social norms, (3) self-efficacy and (4) controllability.

H2a. There will be significant differences between the mean ratings of the four attitude dimensions.H2b. Individuals' professional roles and the clinical setting they work in will have a significant effect on their ratings of the four attitude dimensions.

H3. The four attitude dimensions will be significant predictors for self-reported engagement in the requesting of blood cultures, collection of blood culture samples and use of blood culture results.

H4. Perceptions of the most influential barriers to blood culture sampling will differ across professional roles and clinical settings.

3) Describe the key dependent variable(s) specifying how they will be measured.

1. **Attitude variables:** We will assess beliefs and attitudes pertaining to blood culture sampling via 20 authordesigned questions, created to capture different attitude dimensions that are modelled on the Theory of Planned Behaviour. Each attitude question will be measured on a 7-point likert scale ranging from 1 (strongly disagree) to 7 (strongly agree).

2. Engagement variables: We will assess three single-item, self-reported variables measuring how frequently healthcare staff engage in different aspects of blood culture sampling: (1) requesting samples, (2) collecting samples, and (3) using the results from samples. Variables will be measured on a 5-point likert scale (1= Never, 2 = Hardly any shift, 3 = Some shifts, 4 = Most shifts, 5 = Almost every shift, N/A = this isn't part of my job role).
 3. Barrier variables: We will assess the perceived influences of 29 barriers to blood culture sampling, measured via a 7-point likert scale ranging from 1 (strongly disagree that this factor influences blood culture sampling) to 7 (strongly agree that this factor influences blood culture sampling).

4) How many and which conditions will participants be assigned to?

We will employ a quasi-experimental design, where professional role (doctors vs. advanced clinical practitioners, nurses, paramedics & physician associates vs. healthcare assistants & phlebotomists) and clinical setting (acute medical ward vs. acute surgical ward vs. emergency department vs. critical care unit) will be treated as between-subject IVs.

5) Specify exactly which analyses you will conduct to examine the main question/hypothesis.

H1: We will run a confirmatory factor analysis to test our hypothesized factor structure and validate our attitude questionnaire in the context of blood culture sampling. We will use Maximum Likelihood for our estimation method and assess the goodness of fit of the resulting models using six key statistics: chi-square (χ 2); relative chi-square (CMIN/DF); comparative fit index (CFI); non-normed fit index (NNFI); root mean square error of approximation (RMSEA); and standardized root mean square residual (SRMR). Following identification

Combined Protocol V3.0 22/07/24

of the best model fit, four latent attitude variables will be confirmed, which will be based on the theoretical dimensions of (1) perceived importance, (2) social norms, (3) self-efficacy and (4) controllability in the context of blood culture sampling. For each of these latent variables, factor scores will be calculated by deriving the mean of all constituent variables. We will use these latent variables for our subsequent analyses.

H2a,b: We will run a 3×4 between-within subjects ANOVA to test for interactions and simple main effects of professional role and latent attitude dimension on mean attitude ratings.

We will run a 4×4 between-within subjects ANOVA to test for interactions and simple main effects of clinical setting and latent attitude dimension on mean attitude ratings.

If significant main effects are detected for either ANOVA, we will conduct Bonferroni-corrected pairwise comparisons as follow-up analyses.

H2: We will run three multiple regression analyses, one for each of our engagement variables. For each regression analysis, predictors will be entered hierarchically in blocks.

Block 1: Demographic variables. This will include *age*, *gender* \rightarrow female/other (1), male (0); and *ethnicity* \rightarrow people of colour (1), white (0). **Block 2: Professional variables**. This will include *professional role* \rightarrow healthcare assistants & phlebotomists (2), advanced clinical practitioners, nurses, paramedics & physician associates (1), doctors (0); *clinical setting* \rightarrow acute surgical ward (3); emergency department (2); critical care unit (1); acute medical ward (0); and *seniority* \rightarrow junior (1), senior (0). **Block 3: Attitudes and beliefs**. This will include the latent attitude variables identified in our factor analysis.

H3: We will produce descriptive statistics for the influence ratings pertaining to each of the 29 barriers to blood culture sampling. We will produce an overall ranking of the 3 most influential barriers and separate rankings of barriers for different professional roles and clinical settings.

6) Describe exactly how outliers will be defined and handled, and your precise rule(s) for excluding observations.

We will exclude participants, who took less than five [revise after piloting] minutes to complete the survey. We will exclude participants, who did not complete all 20 attitude questions.

We will exclude participants suspected of "straight-lining". We will test for this separately across the 20 questions measuring attitudes and 29 questions assessing the influence of key barriers by calculating the standard deviation. Participants will be excluded from analyses if their likert ratings from either section have a standard deviation of \leq 0.45.

7) How many observations will be collected or what will determine sample size?

No need to justify decision, but be precise about exactly how the number will be determined.

We considered sample size requirements across our different analyses. Sample size recommendations for scale validation vary depending on the sample type used. For more specific samples (as opposed to samples drawn from the general population), 250-350 participants have been recommended (White, 2021). For our ANOVAs, we ran a G*power calculation for ANOVA (repeated measures, between factors) with 4 groups and 4 measurements, assuming a correlation of up to 0.5. We estimated a power of .80 and an α error probability of .01 to detect a medium effect size f = .25, which returned 236 participants. For our linear multiple regression analysis (fixed model, R² increase) with 10 predictors, we ran a G*power calculation, estimating a power of .80 and an α error probability of .01 to detect a medium effect size f = .15, which returned 160 participants. To satisfy sampling requirements for all types of analyses and to account for potential data loss from incomplete submissions and exclusions, we will recruit up to 400 participants.

8) Anything else you would like to pre-register?

(e.g., secondary analyses, variables collected for exploratory purposes, unusual analyses planned?) N/A

4. Agency UKHS. English surveillance programme for antimicrobial utilisation and resistance (ESPAUR) report 2020-2021. 2021.

5. Trust N. Antibiotic prescribing: Quality Watch 2024 [Available from:

https://www.nuffieldtrust.org.uk/resource/antibiotic-prescribing#background.

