3.1.4. Consent and withdrawal

A participant information sheet (PIS), privacy notice and e-consent form will be integrated within the landing page of the online survey. Only if participants agree to the items on the consent form and indicate their agreement via a tick box can they proceed to the next stages of the survey. The PIS will provide an email address, which they can contact in case of questions. Participants can take as long as they like to decide whether they want to take part, although the survey will be closed once the maximum number of participants has been recruited. Participants will have the option to provide their name and email address and can indicate whether they would like to receive an electronic summary of the study results and/or be entered into a prize draw.

Participants will be informed in the PIS that they can withdraw during the participation by closing the online questionnaire. Their data will not be included in the analysis if they complete less than half of the questionnaire. It will not be possible to withdraw participant data after the questionnaire is completed. This is because individual questionnaire responses will not be identifiable, because no names/email addresses/identification numbers will be stored alongside the research data.

4. Methods of data collection

We will use a newly developed and piloted questionnaire (Appendix A) informed by the Theory of Planned Behaviour (16, 17). The questionnaire contains 3 questions to measure self-reported levels of (1) requesting blood culture samples, (2) taking blood culture samples and (3) using the results from blood culture samples. This is followed by 20 questions pertaining to attitudes and beliefs around blood culture sampling and 30 items listing potential barriers to blood culture sample, which were informed by a literature research and hospital stakeholder visits. All items will require rating, using likert-scales. The questionnaire will conclude with a final open-ended question asking for suggestions about potential interventions to improve blood culture sampling.

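### The questionnaire's factor analysis fixes uncorrected Maximum Likelihood for 20 seven-point items, so its chi-square over-rejects a true four-factor model if the ratings are skewed

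*Protocol*

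**What the plan says.** Part 1b, section 4.1 (Data analysis), refers to its appendix as the complete analysis plan. It calls it Appendix B; it is printed as Appendix 2. The estimator is therefore fixed in this document.

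- **Hypothesis.** Item 2, H1, proposes that "attitudes around blood culture sampling will map on to a four-factor structure proposed by the Theory of Planned Behaviour".
- **Data.** Part 1b, section 4 (Methods of data collection): "This is followed by 20 questions pertaining to attitudes and beliefs around blood culture sampling". Appendix 2, item 3: "Each attitude question will be measured on a 7-point likert scale ranging from 1 (strongly disagree) to 7 (strongly agree". Appendix A lists five items for each of the four dimensions.
- **Estimator and fit.** Item 5, H1: "We will use Maximum Likelihood for our estimation method and assess the goodness of fit of the resulting models using six key statistics". Besides chi-square and the SRMR, these are "relative chi-square (CMIN/DF); comparative fit index (CFI); non-normed fit index (NNFI); root mean square error of approximation (RMSEA".
- **Next step.** Once the best-fitting model has been identified, "four latent attitude variables will be confirmed", and "factor scores will be calculated by deriving the mean of all constituent variables". Those means feed the ANOVAs and the engagement regressions.
- **Sample size.** Item 7 says that for specific samples "250-350 participants have been recommended" for scale validation, and sets recruitment at up to 400.

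No robust or ordinal variant is named, and item 8 registers no further analysis. Item 5 gives no alpha for the chi-square, no cut-off for any index and no rule that a significant chi-square rejects H1.

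**The concern.** The Maximum Likelihood chi-square is meant to test whether the items follow the four-factor structure. Its reference distribution also assumes multivariate normal items. When ratings pile up at one end of a bounded scale, the statistic is inflated even if the structure is exactly right, so it partly tests normality. Relative chi-square, CFI, NNFI and RMSEA are all computed from it.

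Skew is plausible for some items. Eligible respondents request, take or use blood cultures, and items 3.1 and 3.2 (benefit and value of cultures) and 3.6 to 3.8 (norms among respected colleagues and in the unit) invite agreement.

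At stake is the reading of fit for the new questionnaire, which is a secondary research question. Item 5 speaks of more than one resulting model and of finding the best fit. An inflated chi-square could therefore prompt re-specification to remove misfit that is not there. If items moved between dimensions, the mean scores carried into the later analyses would change.

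**Working it through.** The protocol states no alpha, power or rejection rate for the factor analysis, so there is no figure of its own to reproduce.

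**Degrees of freedom.** From the plan: 20 items and four factors. Simple structure with correlated factors is assumed.
- Distinct variances and covariances: 20 × 21 / 2 = 210.
- Free parameters: 20 loadings + 20 residual variances + 6 factor correlations = 46.
- df = 210 − 46 = 164, and the 5% critical value is 194.9.

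**What a just-significant chi-square means for two other indices.**
- Relative chi-square: T/df = 194.9/164 = 1.19.
- RMSEA = √[(T − df)/(df(n − 1))]. At n = 300: √[30.9/(164 × 299)] = 0.025. At n = 400: √[30.9/(164 × 399)] = 0.022.

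So the chi-square can reject while these two indices still look good.

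**Main simulation.** Data came from a true four-factor model with five items per factor, equal loadings of .6, .7 or .8 and factor correlations of .3 to .5. They were cut into seven categories and fitted by plain Maximum Likelihood, with 1,000 replicates per cell and the plan's straight-lining exclusion applied. The skews and loadings are assumptions. Chi-square rejection at nominal 5%, n = 300 / n = 400:

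| Item skew | Loading .6 | Loading .7 | Loading .8 |
|---|---|---|---|
| 0 (symmetric) | 7.3 / 8.0% | 7.8 / 8.4% | 8.6 / 7.3% |
| −0.7 | 14.4 / 13.1% | 18.7 / 19.0% | 26.4 / 29.5% |
| −1.4 | 31.8 / 32.6% | 51.4 / 55.3% | 74.6 / 75.1% |
| −2.3 | 74.0 / 74.8% | 94.7 / 95.8% | 99.7 / 99.4% |
| Mixed, 0 to −2.3 | 21.5 / 20.3% | 34.4 / 37.8% | 70.2 / 76.6% |

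Uncut normal data gave 7–9%. The largest Monte Carlo standard error is √(0.5 × 0.5/1000) = 1.6 percentage points. The mixed row depends heavily on which mixture is assumed.

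**Two smaller runs, both at loading .65.**
- 150 replicates: 28% (n = 300) and 23% (n = 400) at skew −0.9; 58% and 53% at −1.5; 4–9% with normal data.
- 120 replicates at n = 350: about 10% symmetric, 18% mild skew, 60% moderate skew and 14–21% mixed.

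Their standard errors are up to about 4 to 5 points, and they agree with the table in substance.

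**The other indices in the main simulation.** Conventional cut-offs are assumed, because the plan gives none. Entries are ranges over loadings and sample sizes:

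| Index | Skew −1.4 | Skew −2.3 |
|---|---|---|
| CMIN/DF > 2 | 0% | 0–5% |
| RMSEA > .06 | 0% | 0–3% |
| SRMR > .08 | 0% | 0% |
| CFI < .95 | 0–13% | 2–65% |
| NNFI < .95 | 0–20% | 11–74% |

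The worst CFI and NNFI figures are at loading .6 and n = 300.

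**Does scaling repair it?** The Satorra–Bentler scaled chi-square (300 replicates, n = 250 to 400, no exclusions) rejected in about 7–13% when all items were equally skewed. With skews differing across items it was mostly 9–15%, but up to 31% with same-direction skews at loading .8 and up to 64% with opposite-direction skews.

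**The case against.** The strongest objection is that the skew is supposed, not documented. The protocol gives no distribution, and the analysis plan records that no data had been collected. Seven categories do no harm by themselves: symmetric ratings behave like normal data. Only about five items (3.1, 3.2, 3.6 to 3.8) plainly invite agreement. Most of the rest are negative or situational statements about difficulty, unpleasantness or lack of control, and nothing suggests uniform skew over all 20. This stands, and it is why the figures are conditional and why the mixed case matters. That case still showed inflation.

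Second, a reader might take a 50% chi-square rejection rate as a 50% chance that a valid questionnaire fails H1. The plan does not support that reading. Chi-square is one of six statistics and no decision rule is attached to it. At skew −1.4, CMIN/DF, RMSEA and SRMR never crossed the conventional cut-offs.

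Third, the later analyses use item means, not model-based factor scores, so the estimator alone does not alter them. That also stands, short of re-specification.

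What the objection does not remove is that an uncorrected normal-theory statistic is fixed for bounded ordinal ratings, with no alternative named.

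**Conclusion.** The point holds as a conditional weakness. If the ratings are skewed, the plain Maximum Likelihood chi-square rejects a correct four-factor model in about 13–30% of samples at skew of about −0.7 to −0.9, about 30–75% at about −1.4 to −1.5 depending on loadings, and about 14–77% with mixed skew. The fair comparator is about 7–10% at this sample size, not exactly 5%. CFI and NNFI suffer mainly under strong skew.

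The size rests on assumed skews, equal loadings of .6 to .8, a simple four-factor structure and n = 300 to 400. No single rejection rate can be attributed to this study, and none of these figures is a probability of rejecting H1. This is a free or cheap improvement to the plan, not a threat to its main results.

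**What to change.** In Part 1b, Appendix 2, item 5 (H1):

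1. Replace Maximum Likelihood with robust maximum likelihood. Report the scaled chi-square and robust CFI, NNFI and RMSEA, and use the scaled difference test for any model comparison.
2. Pre-specify an ordinal estimator (WLSMV) as a sensitivity analysis, because scaling does not fully restore the nominal rate when skew differs strongly across items.

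The cost is a software option and one extra model run. No new data are needed, and the point estimates under robust maximum likelihood equal those already planned.

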4.1. Data analysis

Data analysis will involve quantitative methods, including: (1) descriptive statistics of beliefs and perceived barriers to blood culture sampling, rated on likert scales; (2) confirmatory factor analysis to test the hypothesized factor structure of our newly developed questionnaire; (3) Analysis of variance (ANOVA) to test for interactions and effects of professional roles and clinical setting on attitude ratings regarding blood culture sampling; (4) multiple regression analyses to identify predictors or self-reported engagement in the blood culture pathway, and (5) qualitative content analysis of an open-ended question around potential interventions to improve blood culture sampling. The full analysis plan can be found as Appendix B.

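### H1 of the staff survey is posed as a test, but the analysis plan fixes the answer at four factors, names no rival model and allows no result in which H1 is not supported

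*Protocol*

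**What the plan says.** Part 1b, section 4.1, announces a "confirmatory factor analysis to test the hypothesized factor structure of our newly developed questionnaire" and points to an appendix for the full analysis plan. That plan is the appendix headed Appendix 2.

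Item 2 of the appendix states H1: "Healthcare staff's attitudes around blood culture sampling will map on to a four-factor structure proposed by the Theory of Planned Behaviour". The four factors are perceived importance, social norms, self-efficacy and controllability.

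Item 5 gives the procedure. It opens with "We will run a confirmatory factor analysis to test our hypothesized factor structure and validate our attitude questionnaire" and adds "We will use Maximum Likelihood for our estimation method". It lists chi-square, relative chi-square, CFI, NNFI, RMSEA and SRMR, with no threshold for any of them. Once the best fit has been identified, "four latent attitude variables will be confirmed, which will be based on the theoretical dimensions" of H1. Scores are then formed as item means and used in the subsequent analyses.

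The number four recurs downstream. Attitude dimension is a four-level factor in both ANOVAs (3×4 and 4×4), the ANOVA sample size in item 7 assumes four measurements, and H2a, H2b and H3 are worded for four dimensions.

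**The concern.** A hypothesis test needs a possible result that counts against the hypothesis. Here the closing statement does not depend on the fit statistics before it. Read literally, a poor fit, or a fit that a simpler model matches, still ends with four confirmed dimensions.

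This matters because the most plausible competitor is in the protocol itself. Section 3 (Theoretical Framework) of the Part 1c/2 protocol describes the Theory of Planned Behaviour with three components: attitudes, subjective norms and perceived behavioural control. Appendix A, section 3, labels both the self-efficacy items (3.11–3.15) and the controllability items (3.16–3.20) as perceived behavioural control. If those ten items measure one thing, following the stated rule would give a wrong answer to the secondary question of whether the questionnaire captures the theory's components. Two ANOVAs and three regressions would then treat one construct as two.

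**Working it through.** **No figure to reproduce.** The plan gives no cut-off, power or error rate for H1. The check is therefore a reading of the rule, a parameter count and a simulation.

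**1. The rule.** Stated purpose: test the structure. Stated evidence: six fit statistics. Stated conclusion: four variables confirmed. No condition links the evidence to the conclusion. Factor correlations, which would show two dimensions merging, are not listed.

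**2. Nesting.** Twenty items give 20 × 21 / 2 = 210 variances and covariances.

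- Four factors: 20 loadings + 20 residual variances + 6 factor correlations = 46 parameters; df = 210 − 46 = 164.
- Three factors (self-efficacy and controllability merged): 20 + 20 + 3 = 43; df = 167.
- One factor: 20 + 20 = 40; df = 170.

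The simpler models are the four-factor model with factor correlations set to 1 and, for three factors, the merged pair sharing the same correlations with the other two. If a simpler model is true, the four-factor model is also correctly specified and will fit well.

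**3. Simulation.** Taken from the plan: 20 items, five per dimension, seven-point scale, maximum likelihood, and n = 250 and 400 (the plan cites 250–350 for scale validation and recruits up to 400). Assumed: loadings .5, .6 and .7; factor correlation .5; continuous or seven-category items; 100 draws per cell. Assumed strict cut-offs: CFI and NNFI ≥ .95, RMSEA ≤ .06, SRMR ≤ .08. Assumed lenient cut-offs: CFI and NNFI ≥ .90, RMSEA ≤ .08, SRMR ≤ .08, relative chi-square ≤ 3. The difference test is at 5%, with 167 − 164 = 3 df against three factors and 170 − 164 = 6 df against one.

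| True structure | Four-factor model passes strict | Passes lenient | Difference test prefers four |
|---|---|---|---|
| One factor | 93–100% | 100% | 3–9% |
| Three factors, merged | 86–100% | 99–100% | 3–11% |
| Four factors | 78–100% | 96–100% | 99–100% |

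Mean CFI was .986–.998 with one true factor and .981–.997 with three. The fit statistics do not separate the three cases; the difference test does.

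**4. Admissibility.** When dimensions merge, the estimated factor correlations are near 1 and often above it. In further runs with loadings of .65 (150 draws per cell, N = 300 and 400), the factor correlation matrix was not positive definite in 58–59% of draws with three true factors and 91–93% with one. Another set (60 draws per cell, N = 250 and 400) gave 42–98% improper solutions across cells.

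**5. Limit of the result.** If the true factors cut across the planned item groups (n = 400), the four-factor model failed both sets of cut-offs in 98–100% of draws at factor correlations of .3–.5. At a correlation of .8 it passed the lenient set in 60–100% and the strict set in 0–58%.

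**6. Effect on later scores.** Two five-item means on the same factor with loadings of .65 correlate at (5 × .65)² / [(5 × .65)² + 5 × (1 − .65²)] = 10.56 / 13.45 = .79. The variance inflation factor for two such predictors is 1 / (1 − .785²) = 2.6.

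**The case against.** The text has points in its favour. It refers to models in the plural and to identifying the best fit, which suggests that some comparison is intended. A reader might infer that no rival will be fitted at all. The document does not support that; it supports only that none is named. The regression section speaks of the latent variables identified in the factor analysis, wording that leaves room for another number. This softens the plan, but it does not supply a result in which H1 fails, and the ANOVAs stay fixed at four levels.

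A reader might also infer that the four-factor model would pass cut-offs whatever the true structure. It would not: the high pass rates apply when planned dimensions merge, and cut-offs mostly detect factors that cut across the item groups at moderate correlations. Many of the passing fits are also inadmissible, so an attentive analyst would often see the problem. The plan, however, does not say what to do then.

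Calling the later predictors near-duplicates would be too strong. At a correlation of about .79 and a variance inflation factor of 2.6, the regressions remain estimable. The ANOVAs would still compare mean ratings by role and setting. The labels and the separate interpretation of the scores are what would be in doubt.

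Finally, H1 is a secondary question. Leaving the matter to a later plan is a weak defence, since section 4.1 presents this appendix as the full analysis plan and item 5 asks for exact analyses.

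**Conclusion.** The concern stands in this form: the plan poses H1 as a test, fixes its outcome at four factors, names no rival and provides no unsupported outcome. That defect is in the wording and needs no simulation. Adding cut-offs for the six listed statistics would not be enough. When planned dimensions merge, about 86–100% of samples would still pass common strict cut-offs, often with factor correlations near or above 1. A difference test against the simpler models would wrongly prefer four factors in about 3–11%.

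These rates rest on assumed loadings of .5–.7, a factor correlation of .5 and conventional cut-offs, none of which the plan states. They do not describe factors that cut across the item groups. The effect is on the validity claim for the questionnaire and on the separate interpretation of self-efficacy and controllability; the survey's other analyses remain usable. The point should be corrected before the data are analysed.

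**What to change.** In Appendix 2, item 5:

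- Replace the unconditional sentence with conditional wording.
- Name three models to be fitted: one factor, three factors (self-efficacy and controllability merged) and four factors.
- Call H1 supported only if the four-factor model meets stated fit criteria, is an admissible solution, and is preferred to both simpler models by a chi-square difference test, scaled because the items are seven-category ratings.
- Report the factor correlations descriptively. A hard bound on their confidence intervals is not advised. With four true factors (N = 300, loadings .65, factor correlation .75), fit cut-offs plus such a bound accepted the true structure in only 13% of samples at a bound of .85 and 70% at .90.
- If four factors are not supported, say so and carry the retained structure forward. With three factors the ANOVAs become 3×3 and 4×3 and the regressions take three scores. With one factor there is no within-subject dimension and H2a cannot be tested.

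The cost is a few sentences and two extra fits on the same data. H1 may be reported as not supported. There is also some risk of losing four factors that are distinct but highly correlated: at a factor correlation of .8 with loadings of .5–.65, the difference test retained them in 82–100% of draws. Appendix 2 states that no data had yet been collected, so on the document's own account the change can be made in advance.
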